#### **7.7 Reporting to the FDA**

The conduct of the study will comply with all FDA safety reporting requirements. **PLEASE NOTE THAT REPORTING REQUIREMENTS FOR THE FDA DIFFER FROM REPORTING REQUIREMENTS FOR HRPO/QASMC.** It is the responsibility of the investigator to report any unanticipated problem to the FDA as follows:

- Report any unexpected fatal or life-threatening adverse experiences associated with use of the drug (i.e., there is a reasonable possibility that the experience may have been caused by the drug) by telephone or fax no later than **7 calendar days** after initial receipt of the information. A life-threatening adverse experience is defined as any adverse drug experience that places the subject (in the view of the investigator) at immediate risk of death from the reaction as it occurred, i.e., it does not include a reaction that, had it occurred in a more severe form, might have caused death.
- Report any serious, unexpected adverse experiences, as well as results from animal studies that suggest significant clinical risk within **15 calendar days** after initial receipt of this information. A serious adverse drug experience is defined as any adverse drug experience occurring at any dose that results in any of the following outcomes:
  - Death

- A life-threatening adverse drug experience
- Inpatient hospitalization or prolongation of existing hospitalization
- A persistent or significant disability/incapacity (i.e., a substantial disruption of a person's ability to conduct normal life functions)
- A congenital anomaly/birth defect
- Any other experience which, based upon appropriate medical judgment, may jeopardize the subject and may require medical or surgical intervention to prevent one of the outcomes listed above

An unexpected adverse drug experience is defined as any adverse drug experience, the specificity or severity of which is not consistent with the current investigator brochure (or risk information, if an IB is not required or available).

All MedWatch forms will be sent by Cantex to the FDA at the following address or by fax:

Food and Drug Administration  
 Center for Drug Evaluation and Research  
 Division of Oncology Drug Products  
 [name]  
 [name]  
 FAX: [name]

Secondary sites must submit a completed MedWatch form to Cantex within **4 calendar days** (for fatal or life-threatening adverse experiences) or **11 calendar days** (for serious, unexpected adverse experiences). Cantex will be responsible for submitting all MedWatch forms to the FDA within the timeframes specified above.

#### **7.8 Timeframe for Reporting Required Events**

Reportable adverse events will be tracked for 30 days after the last dose of DSF.

### **8.0 PHARMACEUTICAL INFORMATION**

#### **8.1 Disulfiram**

##### **8.1.1 Disulfiram Description**

DSF is an alcohol antagonist drug approved by the FDA for the treatment of alcoholism. Its powder is white, odorless, and almost tasteless. It is soluble in water to the extent of about 20mg in 100mL, and in alcohol to the extent of about 3.8 g in 100 mL.

**Molecular formula:** C10H20N2S4

**Chemical name:** bis(diethylthiocarbamoyl) disulfide.

**Molecular weight:** 296.54.

### **8.1.2 Clinical Pharmacology**

DSF is mostly known as an irreversible inhibitor of aldehyde dehydrogenase, which affects alcohol metabolism and causes accumulation of acetaldehyde. However, increasing preclinical studies have shown that DSF is also a proteasome inhibitor, specifically the chymotrypsin-like activity. GBM cells and its stem-like subpopulation (also referred to as CSC) may be more susceptible to the effect of proteasomal inhibition than normal brain cells. DSF is very lipophilic and readily crosses the blood-brain barrier.

### **8.1.3 Supplier**

DSF will be manufactured and provided by Cantex Pharmaceuticals for the study participants.

### **8.1.4 Dosage Form**

DSF is supplied as 40 mg capsules.

### **8.1.5 Storage and Stability**

DSF is dispensed in a tight, light-resistant container. It should be stored at controlled room temperature (20° to 25°C or 68° to 77°F) in its original container to protect from bright light.

### **8.1.6 Disulfiram Administration**

DSF is taken by mouth three times daily. It should be taken with meals to improve absorption. It should not be taken within one hour of TMZ. Patients should not have consumed any alcohol at least 12 hours prior to the first dose. In the rare event of a severe hypersensitivity reaction, discontinue DSF immediately.

## **9.0 CORRELATIVE STUDIES**

Blood samples will be collected for possible future correlative studies. The correlative studies will not be mandated for this protocol. The correlative studies may include assay of inhibition of proteasome activity and analysis of gamma-H2AX via Western blot. Approximately 40 mL of peripheral blood (10 mL into each of 4 green top tubes containing sodium heparin) will be drawn at the baseline, at Week 2 (+2 days/-4 days), and after 1 month of DSF (but before the start of next cycle of TMZ). For patients at Washington University, the blood should be submitted at room temperature to the laboratory of [name], Ph.D. at Washington University. Blood samples should be centrifuged at 6600g for 10 min at 4 °C. Resulting whole blood cell pellets and supernatant should then be stored separately at -80 °C. For other participating institutions outside of Washington University, the whole blood cell pellets and supernatant should be prepared as

above and then frozen at -80 °C. The frozen samples can be shipped to [name] laboratory in dry ice.

## 10.0 STUDY CALENDAR

Screening/baseline evaluations are to be conducted within 2 weeks prior to start of protocol therapy. Scans and x-rays must be done no more than 4 weeks prior to the start of the protocol therapy. Each treatment cycle is 28 days.

	Screening / Baseline	Within 10 Days Before Each Cycle	End of Every Even-Numbered Cycle	End of Treatment	Follow-Up 
Informed consent	X				
H&P incl. neurologic exam, KPS	X	X		X	
Evaluation of corticosteroid usage	X	X			
CBC	X				
LFTs	X				
Brain MRI	X		X 	X	
Temozolomide		Days 1-5 of each cycle 			
Disulfiram		Days 1-28 of each cycle 			
Copper gluconate		Days 1-28 of each cycle 			
AE assessment	X ----- X 				

1. Follow-up will be as clinically indicated. A chart review will be done at 2 years after the last dose of DSF to look for progression and survival.
2. Women of childbearing potential only.
3. A confirmatory MRI should be considered in 4-8 weeks after documentation of complete response (CR) or partial response (PR) if consistent with the institutional standard of care
4. To be taken at bedtime on an empty stomach. Must not be taken within an hour of DSF.
5. To be taken three times a day with meals.
6. AEs will be tracked for 30 days after the last dose of DSF.

## 11.0 DATA SUBMISSION SCHEDULE

Case report forms with appropriate source documentation will be completed according to the schedule listed in this section.

Case Report Form	Submission Schedule
Original Consent Form	Prior to registration
Registration Form	Prior to starting treatment
Eligibility Form	
On-Study Form	
Treatment Form	Every cycle
Toxicity Form	Continuous
Treatment Summary Form	Completion of treatment

Follow Up Form	Day 30 Year 2
Tumor Measurement Form	Baseline End of every even numbered cycle End of treatment
MedWatch Form	See Section 7.0 for reporting requirements

Any queries generated by Washington University must be responded to within 28 days of receipt by the participating site. The Washington University research team will conduct a regular review of data status at all secondary sites, with appropriate corrective action to be requested as needed.

## 12.0 STATISTICAL CONSIDERATIONS

### 12.1 Definition of Primary Endpoint and Analytical Plan

The co-primary endpoints will be objective response rate (ORR) and progression-free survival at 6 months (PFS6). ORR will be defined as the percentage of patients with complete response (CR) or partial response (PR) according to the RANO criteria as described in Section 6.0. PFS6 will be defined as proportion of patients that are free from progressive disease (PD) as per RANO criteria or death at 6 months from the date of the first dose of DSF/Cu. PFS6 and median PFS will be estimated using the Kaplan-Meier product-limit method. For recurrent TMZ-resistant GBM, continuing TMZ should yield ORR of less than 5% and PFS6 of less than 10% (Quinn, et al. 2009). To justify future drug development of DSF for GBM, we hypothesized that the addition of DSF/Cu to TMZ would improve ORR to 20% or increase PFS6 to 30%. The sample size is calculated based on the above hypotheses with one-sided exact test at an approximate  $\alpha$  level of 0.10 and 80% statistical power. At these type I and II error rates, 20 patients will detect a proportion of patients who have ORR significantly higher than 5% or PFS6 significantly higher 10%. Of note, previous phase II study testing addition of OBG (a MGMT inhibitor) to TMZ for TMZ-resistant GBM used similar hypothesis and observed a disappointing ORR of 3% and PFS6 of 9% (Quinn, et al. 2009). This negative phase II study has detailed information on ORR, PFS, and OS as well as associated estimated 95% CIs and will serve as a historical comparison for this study.

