#### **4.7 Duration of Therapy**

If at any time the constraints of this protocol are considered to be detrimental to the patient's health and/or the patient no longer wishes to continue protocol therapy, the

protocol therapy should be discontinued and the reason(s) for discontinuation documented in the case report form.

In the absence of treatment delays due to adverse events, DSF treatment may continue until:

- Documented and confirmed disease progression
- Death
- Adverse event(s) that, in the judgment of the investigator, may cause severe or permanent harm or which rule out continuation of study drug
- General or specific changes in the patient's condition render the patient unacceptable for further treatment in the judgment of the investigator
- Suspected pregnancy
- Serious noncompliance with the study protocol
- Lost to follow-up
- Patient withdraws consent
- Investigator removes the patient from study
- The sponsor (Cantex), the investigator, or the investigator's institution decides to close the study

In the case of tumor progression, both TMZ and DSF-Cu should be discontinued, and patient should be considered for second-line therapy. If TMZ is temporarily withheld due to toxicity, DSF-Cu should be continued until TMZ may be resumed again. If TMZ is discontinued, DSF-Cu may be continued as per the discretion of the treating physician. If DSF-Cu is discontinued due to toxicity, TMZ may be continued as per the discretion of the treating physician.

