#### **4.8 Duration of Follow-up**

Patients are evaluated for adverse events for 30 days after the last dose of DSF-Cu or until death, whichever occurs first. Patients removed from study for unacceptable adverse events will be followed until resolution or stabilization of the adverse event. Follow-up after the conclusion of the study participation will be per routine clinical care. Two years after the patient goes off study, the patient's chart will be reviewed to collect data on progression and survival.

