Progression	Defined by any of the following: 
 
<math>\geq 25\%</math> increase in sum of the products of perpendicular diameters of enhancing lesions compared with the smallest tumor measurement obtained either at baseline (if no decrease) or best response, on stable or increasing doses of corticosteroids*. The absolute increase in any dimension must be at least 5mm when calculating the products.
 
Significant increase in T2/FLAIR non-enhancing lesion on stable or increasing doses of corticosteroids compared with baseline scan or best response after initiation of therapy* not caused by comorbid events (e.g. radiation therapy, demyelination, ischemic injury, infection, seizures, postoperative changes, or other treatment effects).
 
Any new measurable lesion.
 
Clear clinical deterioration not attributable to other causes apart from the tumor (e.g. seizures, medication adverse effects, complications of therapy, cerebrovascular events, infection, and so on) or changes in corticosteroid dose.
 
Failure to return for evaluation as a result of death or deteriorating condition; or clear progression of non-measurable disease.
 

- NOTE. All measurable and non-measurable lesions must be assessed using the same techniques as at baseline.
- Abbreviations: MRI, magnetic resonance imaging; FLAIR, fluid-attenuated inversion recovery.
- Stable doses of corticosteroids include patients not on corticosteroids.

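### With 20 patients, no PFS6 cutoff gives the planned alpha of about 0.10 with 80% power, and section 12.1 does not say which cutoff applies

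*Combined protocol and SAP*

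**What the plan says.** Section 12.1 names ORR and PFS6 as co-primary endpoints. The reference rates on continued temozolomide are 5% for ORR and 10% for PFS6. The hypothesis is that adding the study drugs "would improve ORR to 20% or increase PFS6 to 30" per cent. The sample size is calculated "with one-sided exact test at an approximate" alpha "level of 0.10 and 80% statistical power", and the section concludes that "20 patients will detect a proportion of patients who have ORR significantly higher than 5% or PFS6 significantly higher 10" per cent.

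Neither section 12.1 nor any other section gives a rejection number, an attained alpha or power, or an error rate for the either-endpoint hypothesis.

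On the estimator, section 12.1 says that "PFS6 and median PFS will be estimated using the Kaplan-Meier product-limit method". Three other places bear on unknown 6-month status:

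- Section 5.0 counts as progression "Failure to return for evaluation as a result of death or deteriorating condition".
- Section 4.8 says that two years after a patient goes off study the "chart will be reviewed to collect data on progression and survival".
- Section 4.7 lists reasons for stopping treatment that include "Patient withdraws consent" and loss to follow-up.

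**The concern.** An exact binomial test on 20 patients can attain only a few alpha levels, so a nominal level does not settle the decision rule unless the cutoff is also given. For PFS6 the two candidate cutoffs lie on either side of 0.10, and neither is close to it. Read strictly, the rule is at least 5/20, with less power than claimed. Read with the tolerance that the word approximate allows, 4/20 with p = 0.133 could be presented as significant.

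Section 4.0 describes a single-arm, open-label trial, and sections 1.8 and 12.1 tie its result to whether the drug is developed further. With no written cutoff, that decision could turn on a choice made after the data are known.

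There is also a smaller gap. An exact test needs a count of successes out of a fixed number of patients, and a Kaplan-Meier estimate with censoring does not supply one.

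**Working it through.** **Inputs, all from section 12.1:** n = 20; ORR p0 = 0.05, p1 = 0.20; PFS6 p0 = 0.10, p1 = 0.30; one-sided exact test, alpha about 0.10, power 80%.

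**Formula.** For a rule that declares success at r or more of n, alpha = P(X ≥ r | n, p0) and power = P(X ≥ r | n, p1), with X binomial.

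**Reproducing the plan's figure at n = 20**

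| Endpoint | Cutoff | Alpha | Power |
|---|---|---|---|
| ORR | ≥2/20 | 0.264 | 93.1% |
| ORR | ≥3/20 | 0.076 | 79.4% |
| ORR | ≥4/20 | 0.016 | 58.9% |
| PFS6 | ≥3/20 | 0.323 | 96.5% |
| PFS6 | ≥4/20 | 0.133 | 89.3% |
| PFS6 | ≥5/20 | 0.043 | 76.2% |
| PFS6 | ≥6/20 | 0.011 | 58.4% |

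ORR at ≥3/20 matches the stated design to within a point of power. No PFS6 row does. The one-sided 90% exact lower bound is 9.0% for 4/20, which does not exclude 10%, and 12.7% for 5/20, which does.

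**Combining the endpoints.** The joint distribution of ORR and PFS6 is not given, so two assumed cases are used. In the independent case, P(either) = a + b − ab, where a and b are the two success probabilities. In the nested case every responder is progression-free at 6 months, so that, given x PFS6 successes, responders are Bin(x, ORR/PFS6).

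*The cutoff alone decides the trial.* This happens when PFS6 is exactly 4/20 and ORR is at most 2/20:

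| True rates | P(PFS6 = 4/20) | Independent | Nested |
|---|---|---|---|
| PFS6 10%, ORR 5% | 0.0898 | × 0.9245 = 8.3% | × 0.6875 = 6.2% |
| PFS6 30%, ORR 20% | 0.1304 | × 0.2061 = 2.7% | × 0.4074 = 5.3% |
| PFS6 30%, ORR 5% | 0.1304 | × 0.9245 = 12.1% | × 0.9838 = 12.8% |

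*At least one success, with ORR ≥3/20:*

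| True rates | PFS6 cutoff | Independent | Nested |
|---|---|---|---|
| Both null | ≥5/20 | 0.0755 + 0.0432 − 0.0755 × 0.0432 = 11.5% | 9.5% |
| Both null | ≥4/20 | 0.0755 + 0.1330 − 0.0755 × 0.1330 = 19.8% | 15.7% |
| Both alternatives | ≥5/20 | 95.1% | 86.1% |
| PFS6 30%, ORR 5% | ≥5/20 | 78.0% | 76.5% |

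Whatever the dependence, the combined false-positive chance cannot exceed the sum of the two: 0.0755 + 0.0432 = 11.9% with ≥5/20, and 0.0755 + 0.1330 = 20.8% with ≥4/20.

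**Unknown 6-month status counted as failure.** The documents give no rate, so 5% and 10% are assumed. The effective PFS6 rate becomes 0.30 × 0.95 = 0.285 or 0.30 × 0.90 = 0.27. Power at ≥5/20 falls from 76.2% to 71.5% or 66.2%.

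**Neighbouring sizes.** PFS6 at ≥4/18 gives 0.098 and 83.5%; ≥5/21 gives 0.052 and 80.2%. ORR at ≥3/21 gives 0.085 and 82.1%. The smallest size at which both endpoints meet alpha of at most 0.10 and power of at least 80% is therefore 21.

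**The case against.** The plan claims only an approximate alpha, and exact tests move in steps. Twenty lies between two sizes that work for PFS6, 18 and 21; the shortfall under the strict rule is 3.8 points, and one more patient would remove it. That stands: this is not a badly undersized trial.

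A rule can also be inferred. A test at 0.10 rejects at 5/20 (p = 0.043) and not at 4/20 (p = 0.133), and the word approximate sits in the sentence about sample size. This is the more natural reading, but it is not the only one. It is also the reading under which the stated power is not met.

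The text says "or" and never says 80% for each endpoint. If power means success on either endpoint with both alternatives true, it is 86.1–95.1% even with ≥5/20. This too stands, and it confines the power concern to the case where PFS6 improves and ORR does not (76.5–78.0%).

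On missing status, sections 5.0 and 4.8 cover much of the ground. What stays open is withdrawal or loss for reasons other than death or deterioration, where the chart review finds nothing. Counting those patients as failures is a choice, and it could cost more power than the shortfall described here.

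**Conclusion.** The concern holds and should be fixed. At n = 20 no PFS6 cutoff delivers the stated pair of error rates, and the documents do not say which cutoff applies. The per-endpoint figures are exact and rest only on the rates in section 12.1.

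The practical weight is moderate. The ambiguity bites only at exactly 4/20 with ORR at most 2/20, which has a probability of 2.7–12.8% across the scenarios above. That range and the combined error rates depend on the assumed relation between the endpoints; the ceilings of 11.9% and 20.8% do not. The missing-status point is secondary, and the conclusion does not depend on it.

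**What to change.** Keep 20 patients and add the following to section 12.1 before the 6-month results are known:

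1. ORR succeeds at ≥3/20 (alpha 0.076, power 79%).
2. PFS6 succeeds at ≥5/20 (alpha 0.043, power 76%). This makes 0.10 a ceiling for each endpoint and replaces the 80% claim for PFS6.
3. Success on either endpoint is enough. The combined false-positive chance is 9.5% if the endpoints are nested, 11.5% if independent, and at most 11.9%.
4. The exact PFS6 test counts all treated patients, with undocumented 6-month status counted as failure. The Kaplan-Meier PFS6 is descriptive.

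The cost is a few sentences and an honest statement of lower PFS6 power: 76.2% with complete follow-up, and less if some patients are undocumented. Item 4 is the most open to debate; another rule would do if it is written in advance.

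If 80% per endpoint is to be kept, 21 patients with ≥3/21 and ≥5/21 achieve it. The combined false-positive chance is then 0.0849 + 0.0522 − 0.0849 × 0.0522 = 13.3% if independent, or 10.8% if nested.

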### 12.2 Definition of Secondary Endpoints and Analytical Plans

The secondary endpoints will be toxicity, OS, and pharmacodynamic effect of proteasome inhibition.

1. Toxicities that are possibly/probably/definitively related to DSF will be graded by NCI CTCAE version 4.0 and will be tabulated by type and grade.
2. OS will be measured from the date of the first dose of DSF/Cu to the date of death or, otherwise, the last follow-up date on which the patient was reported alive.

Median OS and OS12 (proportion of patients that are alive at 12 months) will be estimated using the Kaplan-Meier product-limit method.

3. Proteasome inhibition of DSF/Cu will be performed on peripheral blood cells using fluorometric 20S proteasome assay as described in section 10.0. They will be normalized to the baseline activity and reported as mean and SD (standard error).
4. Gamma-H2AX expression, a marker of DNA damage, will be analyzed by Western blot. The expression level will be normalized to the baseline activity and reported as mean and SD.

[figure not shown]

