In a previous phase I study of 500-1000 mg DSF in combination with adjuvant TMZ in newly diagnosed GBM patients after chemoradiotherapy, grade 2-3 toxicities that were attributed to DSF included delirium, ataxia, dizziness, neuropathy, and fatigue (Table 1). Higher dose of 1000 mg DSF per day could not be tolerated due to relatively fast onset of delirium and ataxia within the first month of therapy. Therefore, it was determined that 500 mg per day of DSF is the MTD in combination with adjuvant TMZ. However, even at the MTD of 500 mg per day, 2 of 7 patients eventually stopped DSF due to possibly DSF-related toxicity. One patient developed grade 3 delirium after 55 days of DSF; another patient developed grade 3 motor neuropathy (lower extremity weakness and foot drop). Both toxicities resolved after discontinuing DSF (Huang, et al. 2016).

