### 2.2 Secondary Objectives

1. To evaluate the safety and tolerability of DSF-Cu administered TID when given concurrently with TMZ.
2. To determine OS of TMZ-resistant GBM patients treated with DSF-Cu in combination with TMZ.

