## 4.0 TREATMENT PLAN

This multi-center study is a single arm, open-label, phase II study of DSF-Cu in combination with TMZ for recurrent TMZ-resistant GBM patients after their first relapse from TMZ.

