### 4.2 Disulfiram and Copper Dosing

Two study drugs will be provided: disulfiram in 40 mg capsules and copper gluconate in 1.5 mg capsules. DSF will be given at 80 mg (two capsules) three times daily with meals. Copper gluconate will be taken with each dose of DSF at a dose of 1.5 mg (one capsule) to improve the potential effect of DSF on GBM tumors. Although Washington University's previous phase 1 study has demonstrated MTD of DSF to be 500 mg per day in combination with TMZ, the current protocol uses a TID administration with concurrent Cu, which may improve absorption and bioavailability. Thus, the DSF dose will be a total of 240 mg per day. If administration of DSF and Cu together causes gastrointestinal discomfort, then Cu will be administered 30 minutes before the DSF dose. If a patient misses a dose, s/he should be instructed not to make up that dose but should instead resume dosing with the next scheduled dose. Patients will be instructed to bring all unused drug and the completed medication diary (Appendix B) to each study visit for assessment of compliance.

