**Table 2: Potential Adverse Events Related to DSF**

MedDRA Term	Frequency: Likely: greater than 10% Less Likely: 1-10% Rare: 1% or less
Neoplasms	Rare: Tumor necrosis
Blood and lymphatic system disorders	Rare: Neutropenia, anemia, leukopenia, thrombocytopenia, lymphopenia (likely due to TMZ)
Immune system disorders	Rare: Hypersensitivity
Metabolism and nutrition disorders	Likely: Alcohol intolerance, metallic or garlic-like aftertaste
Psychiatric disorders	Less Likely: psychosis, delirium (need to rule out tumor progression)
Nervous system disorders	Likely: Drowsiness, headache, confusion Less Likely: ataxia, gait disturbance, peripheral neuropathy Rare: Extrapyrarnidal symptoms
Eye disorders	Rare: Optic neuritis
Cardiac disorders	Less Likely: Tachycardia, hypotension (need to rule out DSF-alcohol reaction)
Respiratory, thoracic, and mediastinal disorders	Less Likely: Dyspnea (need to rule out DSF-alcohol reaction)
Gastrointestinal disorders	Likely: Nausea, vomiting, diarrhea Less Likely: constipation (likely due to temozolomide)
Hepatobiliary disorders	Rare: Hepatitis
Skin and subcutaneous tissue disorders	Less Likely: Allergic dermatitis
Musculoskeletal	Rare: Arthralgia, myalgia
Renal and urinary disorders	Rare: Dysuria, hematuria

MedDRA Term	Frequency: Likely: greater than 10% Less Likely: 1-10% Rare: 1% or less
Reproductive system	Less likely: impotence
General disorders	Likely: Fatigue

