#### **6.2 Disulfiram Dose Modifications**

If a patient experiences any grade 2 or higher non-hematologic toxicity considered by the investigator to be possibly, probably, or definitely related to DSF, the dose of DSF may be decreased by 50% (i.e., from 80 mg TID to 40 mg TID) once. Special attention should be paid to neurological symptoms such as delirium/psychosis, gait disturbance/ataxia, and peripheral neuropathy. A grade 2 toxicity of the above neurological symptoms should prompt a consideration for further work-up and dose reduction. No second dose reduction is allowed—if a second dose reduction is required, DSF and Cu will be discontinued and the patient will be taken off study. Of note, hematologic toxicity is uncommon for DSF and is likely related to TMZ.

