## 7.2 Unanticipated Problems

### **Definition:**

- unexpected (in terms of nature, severity, or frequency) given (a) the research procedures that are described in the protocol-related documents, such as the IRB-approved research protocol and informed consent document; and (b) the characteristics of the subject population being studied;
- related or possibly related to participation in the research (in this guidance document, possibly related means there is a reasonable possibility that the incident, experience, or outcome may have been caused by the procedures involved in the research); and
- suggests that the research places subjects or others at a greater risk of harm (including physical, psychological, economic, or social harm) than was previously known or recognized.

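### The one planned toxicity table keeps only events attributed to DSF, although the safety objective concerns DSF-Cu given with TMZ, so it may understate toxicity seen on the combination

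*Combined protocol and SAP*

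**What the plan says.** Section 2.2 gives the first secondary objective as "To evaluate the safety and tolerability of DSF-Cu administered TID when given concurrently with TMZ". Section 4.0 describes the trial as a "single arm, open-label, phase II study of DSF-Cu in combination with TMZ". Section 4.2 treats copper as a study drug in its own right: "Two study drugs will be provided: disulfiram in 40 mg capsules and copper gluconate in 1.5 mg capsules".

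The analysis of toxicity is a single sentence, item 1 of section 12.2: "Toxicities that are possibly/probably/definitively related to DSF will be graded by NCI CTCAE version 4.0 and will be tabulated by type and grade". Neither copper nor TMZ is named in it. No table of all-cause events, serious events, or events related to copper or TMZ is planned elsewhere.

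On likely cause, section 6.2 remarks that "hematologic toxicity is uncommon for DSF and is likely related to TMZ". Table 2 makes a similar comment beside the cytopenias it lists as rare potential DSF events. For psychosis and delirium, Table 2 asks that tumour progression be excluded.

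**The concern.** The objective asks what happens to patients on the combination. The planned table answers a narrower question: which of those events an investigator, knowing the treatment, was willing to link to DSF. In a single arm there is no control rate against which that judgement can be checked.

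An event judged unrelated to DSF, because it was put down to TMZ or to the tumour, would not appear. A low or empty row could then mean that few events occurred or that they were attributed elsewhere, and a reader of the report could not tell which. Copper adds a second gap if the sentence is taken at its word.

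What is at stake is the description of safety for a regimen being considered for further study. The co-primary endpoints, the sample size and any decision rule are untouched.

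**Working it through.** The plan states no figure on this point, so there is nothing to reproduce. The check compares the sections.

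1. **Target (2.2).** The subject is DSF-Cu, three times daily, with TMZ running concurrently.

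2. **Analysis (12.2, item 1).** The table is restricted to events at least possibly related to DSF. This is narrower than the target.

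3. **Collection.** Section 7.1 defines an adverse event without reference to cause and applies CTCAE version 4.0 to all toxicity reporting. Sections 4.4 and 4.8 follow patients for 30 days after the last DSF-Cu. Section 11.0 has a Toxicity Form submitted continuously. None of these is limited by attribution, so collection is broader than analysis and the gap lies in the analysis plan alone.

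4. **What can drop out.** An event is lost only if it is rated unrelated to DSF. Blood-count events (Table 2, 6.2) and constipation (Table 2) are said to be likely due to TMZ. For neurological events, Table 2 and section 4.5.3 direct attention to tumour progression as an alternative cause. These are the places where loss is plausible.

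5. **Copper.** The text points both ways.
   - For shorthand: section 4.5 bars investigational therapy other than DSF, which taken literally would bar the trial's own copper. Section 7.8 ends tracking at the last dose of DSF, where 4.4 and 4.8 say DSF-Cu.
   - For a literal reading: items 2 and 3 of the same section 12.2 write DSF/Cu, and section 6.2.1 speaks of toxicity from DSF-Cu.
   - On either reading the filter in step 2 remains.

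6. **Size.** Let A be the number of patients with a given event from any cause, and s the share of them with at least one such event rated at least possibly related to DSF. The planned table shows A × s patients. The documents do not give s, so it can lie anywhere from 0 to 1. As an illustration only, take the planned 20 patients (12.1) and assume A = 4, an all-cause rate of 4/20 = 20%:
   - s = 0: 4 × 0 = 0, table shows 0/20 = 0%
   - s = 0.5: 4 × 0.5 = 2, table shows 2/20 = 10%
   - s = 1: 4 × 1 = 4, table shows 4/20 = 20%, no loss

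   Both A and s are assumptions. The arithmetic shows how the filter works and is not an estimate for this trial.

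**The case against.** The strongest reply is that an attribution table fits the objective. DSF-Cu is the thing being evaluated. TMZ is the setting: the sponsor does not supply it (4.3), and its dose changes are left to routine care (6.1). An all-cause table from one arm cannot separate toxicity added by DSF-Cu from that of TMZ alone. This is a fair reason to keep the attributed events. It is not a reason to report only those events when the objective names concurrent use.

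Second, the bar for inclusion is low. A possible relation suffices, and section 7.2, writing about unanticipated problems, explains that "possibly related means there is a reasonable possibility". Section 7.7 uses similar language for association with the drug. The loss may therefore be small. That stands. The governing attribution definitions sit in external guidance cited in 7.1, so the bar cannot be fixed from these documents.

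Third, item 1 does not forbid further tables and the data will exist, so nothing is irretrievably lost. That also stands and limits the severity. However, a table added later would be chosen with the results in view.

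Three stronger readings are tempting, and the documents do not support them:

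- **That the protocol steers blood-count events away from DSF.** Calling an event likely due to TMZ does not bar a rating of possibly related to DSF, and Table 2 lists cytopenias among potential DSF events.
- **That the earlier phase I study shows the filter at work.** Its Table 1 has no blood-count row, but a missing row is not a reported zero. Section 1.6 says only that "grade 2-3 toxicities that were attributed to DSF included delirium, ataxia, dizziness, neuropathy, and fatigue", a list that need not be complete. No rate or upper limit should be drawn from it.
- **That copper is certainly left out.** The wording is ambiguous, as step 5 of the working shows.

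**Conclusion.** The mismatch holds: one table, filtered by attribution to DSF, is planned for an objective about DSF-Cu given with TMZ. The table may understate the toxicity seen on the combination. A reader might go further and infer that it will, but that depends on how investigators attribute events, and the documents give no share. The loss ranges from none (every affected patient has an event rated at least possibly related to DSF) to complete (none has).

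The conclusion assumes that item 1 is followed as written and that no other safety table exists outside the supplied text. It does not depend on how the copper wording is read. It concerns a descriptive secondary endpoint only. I would class it as a cheap improvement.

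**What to change.** Reword item 1 of section 12.2 along these lines: all adverse events from the first dose to 30 days after the last dose of DSF-Cu will be graded by CTCAE version 4.0 and tabulated by type and worst grade per patient, regardless of attribution; events at least possibly related to DSF or Cu will be shown as a subset. Naming Cu in the subset also settles the copper ambiguity. The change is best made before results are known.

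Costs and limits:

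- Slightly more tabulation. Collection, grading and forms stay as planned.
- The reported rates can only stay the same or look less favourable than under the filter.
- The all-cause counts will include symptoms of tumour progression. Within the 30-day window they will also include events under TMZ alone or under later therapy, both of which section 4.7 allows. The report should say so. The related subset helps, but it rests on the same open-label attribution.
- In a single arm the all-cause table describes toxicity on the combination. It cannot isolate what DSF-Cu adds to TMZ.
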